4.2.10.3 Vital signs

Vital signs will be summarised using descriptive statistics for absolute value at each time point by treatment group, together with the corresponding changes from baseline during DB period and during OLE period, respectively.

Baseline to maximum post-baseline and baseline to minimum post-baseline value shift tables will be generated, as applicable for each parameter and will include patients with both baseline and post-baseline data.

4.2.10.4 ECG

A shift table will be produced to display the overall ECG evaluation of normal, abnormal – not clinically significant, abnormal – clinically significant, and not done. For this purpose, borderline (also recorded on the eCRF) will be grouped with normal. Shift tables will present baseline and last observed post-baseline value over safety analysis set during the DB period.

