8.2.4. Electrocardiograms

Electrocardiograms are to be performed at Visit 1 to assess eligibility for this study, and then at V7 (week 24) and V11 (week 56). In all patients, the printouts of the ECG will be collected and signed, dated and stored at the study centre along with a signed and dated copy (if the printouts are not on archive-quality paper).

A 12-lead ECG will be taken in supine position, after the patient has been resting for at least 5 minutes. The assessment should be performed before interventions with the patient (e.g. endoscopy, blood draw). Patients with any ECG abnormalities should be evaluated by the Investigator or qualified delegate to determine if each abnormality is clinically significant. It is highly recommended that the same machine is used for assessment throughout the patient's participation in the study.

The overall evaluation of the ECG will be recorded into eCRF. For abnormal ECG, the reason and clinical significance should also be recorded.

A patient with a clinical significant abnormal finding on the ECG at V1, assessed by PI, should be screen failed.

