9.4.2.2. Analyses of safety variables

Safety data will be presented using descriptive statistics unless otherwise specified. In general, the baseline value for statistical analysis is the last non-missing value prior to administration of the first dose of IP. Details will be described in the SAP.

Adverse Events

Adverse events will be coded using the most recent version of the Medical Dictionary for Regulatory Activities (MedDRA) that will have been released for execution at AZ/designee. AEs will be presented for each treatment group by SOC and/or PT covering number and percentage of patients reporting at least one event and number of events where appropriate.

An overview of AEs will present for each treatment group the number and percentage of patients with any AE, AEs with outcome of death, serious AEs, and AEs leading to discontinuation of IP. Separate AE tables will be provided taken into consideration

relationship as assessed by the investigator, intensity, seriousness, death and events leading to discontinuation of IP. An additional table will present number and percentage of patients with most common AEs (frequency of $\geq 3\%$). Key patient information will be presented for patients with AEs with outcome of death, serious AEs, and AEs leading to discontinuation of IP. An AE listing for the safety analysis set will cover details for each individual AE. Full details of AE analyses will be provided in the SAP.

The following events are considered treatment emergent:

- Adverse events with an onset date on or after first dose of IP
- Worsening of pre-existing events on or after first dose of IP

Vital signs

Vital sign parameters will be presented for each treatment group. Summary statistics for continuous variables cover n, Min, median, and Max. For each scheduled post-baseline visit, descriptive statistics for all vital sign parameters will be presented for observed values and change from baseline. Details of vital sign analyses will be provided in the SAP.

Clinical Laboratory Measurements

Laboratory data will be summarized per treatment group by presenting shift tables using normal ranges (baseline to most extreme post-baseline value) and by presenting summary statistics of observed and change from baseline values. Details of laboratory data analyses will be provided in the SAP.

ECG

Summary statistics for the overall evaluation of ECG will be tabulated per treatment group. Details of ECG analyses will be provided in the SAP.

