4.2.10.2 Laboratory data

All protocol-specified continuous laboratory parameters will be summarised descriptively for absolute value at each time point by treatment group, together with the corresponding changes from baseline. This will be provided for the DB period at primary DBL as well as for the OLE period at final DBL. All parameters will be summarised in SI units unless otherwise specified.

Central laboratory reference ranges will be used for the identification of abnormalities, and a shift table will be produced for each laboratory parameter to display low, normal, and high

values. The shift tables will present baseline and maximum/minimum post-baseline value, as applicable for each parameter and will include patients with both baseline and post-baseline data. Shift tables will use all available data during DB period and during OLE period, respectively.

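### The ECG shift table keeps only the last post-baseline reading, so a Week 24 abnormality that has resolved by Week 56 is absent from the only ECG display SAP 4.2.10.4 defines

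*SAP*

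**What the plan says.** ECG is a named safety variable in the objectives tables of both documents. Protocol 8.2.4 and Table 2 schedule ECGs at Visit 1, Week 24 and Week 56; the last column of Table 2 also serves as the visit for early IP discontinuation. The investigator's overall evaluation is what is recorded.

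SAP 4.2.10.4 plans a shift table with the categories "normal, abnormal – not clinically significant, abnormal – clinically significant, and not done", and adds: "Shift tables will present baseline and last observed post-baseline value over safety analysis set during the DB period". It also states that "borderline (also recorded on the eCRF) will be grouped with normal".

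The other safety shift tables use extremes. For laboratory data, SAP 4.2.10.2 says "The shift tables will present baseline and maximum/minimum post-baseline value, as applicable for each parameter", following Protocol 9.4.2.2, which specifies "baseline to most extreme post-baseline value". For vital signs, SAP 4.2.10.3 says "Baseline to maximum post-baseline and baseline to minimum post-baseline value shift tables will be generated". Both of those sections also plan a descriptive summary at each time point. SAP 4.2.10.4 plans none for ECG.

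Three other provisions matter. SAP 3.8.4 sends new or worsened ECG findings judged clinically significant to AE reporting unless they are clearly due to the disease under study. SAP 3.1.2 puts all values in data listings. The same section says site-reported visit numbers will be used for ECG in a visit-based summary.

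**The concern.** A safety shift table is meant to show what happened to patients while exposed. With two scheduled post-baseline readings and a last-value rule, the earlier one counts only when the later one is missing. A patient who is normal at baseline, abnormal at Week 24 and normal at Week 56 is tabulated as normal throughout.

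The rule can also select the less relevant reading in patients who stop IP. Protocol 7.1.1 asks them to continue visits to Week 56, and SAP 3.1.1 runs the double-blind period to that visit for patients who do not enter the OLE. Their last ECG may be taken well after the last dose, and it then displaces the ECG taken on or near treatment.

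At stake is how completely ECG changes can be compared between arms. No efficacy result or protocol requirement depends on it.

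**Working it through.** The plan gives no figure to reproduce. The check sets the rules side by side, counts the cases the last-value rule hides, and bounds the effect.

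**1. Rules compared**

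| Variable | Post-baseline value in shift table | By-visit summary in the same section |
|---|---|---|
| Laboratory (SAP 4.2.10.2) | maximum/minimum | yes |
| Vital signs (SAP 4.2.10.3) | maximum and minimum | yes |
| ECG (SAP 4.2.10.4) | last observed | none defined |

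**2. Which result pairs are hidden**

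Take the three evaluable categories in order: normal (N), abnormal not clinically significant (NCS), abnormal clinically significant (CS). Two visits give 3 × 3 = 9 ordered pairs. Week 24 is worse than Week 56 in three of them:

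- NCS then N
- CS then N
- CS then NCS

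A last-value table shows the Week 24 category in none of the three; a worst-value table shows it in all three. In the other six pairs the two rules agree. If the Week 56 ECG is missing and no other ECG follows, Week 24 is the last value and is shown.

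**3. What reaches another summary**

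Two of the three hidden pairs involve a CS result at Week 24. Protocol 8.2.4 says a patient with a clinically significant ECG at Visit 1 should be screen failed, so a later CS result should normally be new or worsened. It then goes to AE reporting under SAP 3.8.4, unless clearly due to the disease under study, and enters the SAP 4.2.10.1 tables. The remaining pair, NCS then N, has no summary by arm defined in SAP 4.2.10.4 and would be found only in listings.

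**4. Off-treatment readings**

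Suppose a patient's last dose is at Week 24. The IP-discontinuation visit, with its ECG, falls within 8 weeks of that dose, that is by Week 32. If the patient attends Week 56, that ECG is taken 56 − 24 = 32 weeks after the last dose, and it is the one tabulated.

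**5. Size**

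Let p be the probability of an abnormal reading at each visit. The proportion shown is p under the last-value rule and P(abnormal at either visit) under the worst-value rule. The difference is P(abnormal at Week 24 and not at Week 56).

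- Full persistence (the same patients abnormal at both visits): difference = 0.
- Independence: 1 − (1 − p)² − p = p(1 − p).

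The documents give no p. With p = 5% assumed, independence gives 1 − 0.95² = 9.75% against 5.0%, a difference of 4.75 percentage points. For non-negative correlation between visits the range is therefore **0 to 4.75 percentage points**. This is a count within an arm and says nothing about a difference between arms.

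**The case against.** The strongest reply is that the plan does not discard the Week 24 ECG. New or worsened clinically significant findings become AEs whether or not they later resolve, and every value is listed. SAP 3.1.2 presupposes a visit-based ECG summary, and Protocol 9.4.2.2 promises summary statistics of the overall evaluation without restricting them to the last value. This largely stands. A reader might infer that resolved abnormalities vanish from the safety report, or that half of a completer's scheduled ECGs are ignored; the documents support that only for the shift table. The reply does not close the gap, because SAP 4.2.10.4 never defines the visit-based summary and a listing gives no comparison by arm.

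It can also be said that maximum and minimum suit numeric variables with reference ranges, whereas ECG is a categorical judgement, and that the protocol leaves ECG detail to the SAP. Correct: the last-value rule contradicts nothing in the protocol, and the different rules are not an error in themselves. But the ECG categories have a natural order, so a worst value is well defined, and no reason is given for preferring the last.

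A reader might also want to treat the grouping of borderline with normal as part of the same fault. The documents do not support that. The grouping is openly pre-specified and would apply equally under a worst-value rule, so it does not cause the Week 24 loss. Showing borderline separately is a presentation preference.

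Finally, the stakes are low: none of the AEs of interest in SAP 4.2.10.1 is cardiac. That stands, and it limits the priority of the point.

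**Conclusion.** The point holds in limited form. The one ECG display defined in SAP 4.2.10.4 cannot show a Week 24 abnormality that has improved by Week 56, and it may represent a patient who stopped IP by an off-treatment ECG. The loss is mainly of transient abnormalities judged not clinically significant, which have no defined summary by arm. Transient clinically significant results are lost from the ECG table but should still appear among the AEs, subject to the disease-under-study exception.

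The difference from a worst-value table is 0 to 4.75 percentage points of patients per arm if p = 5%; it depends on that assumed rate and on how far abnormalities persist between visits. The conclusion itself rests on the wording of the SAP and not on this figure. It is a minor improvement to safety reporting and does not identify an error against the protocol.

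**What to change.** In SAP 4.2.10.4, tabulate baseline against the worst post-baseline evaluation in the double-blind period, ordered normal, abnormal not clinically significant, abnormal clinically significant, using all scheduled and unscheduled ECGs. This can replace the last-value shift or stand beside it. Reserve the not-done category for patients with no evaluable post-baseline ECG.

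Alternatively, define in SAP 4.2.10.4 the visit-based ECG summary that SAP 3.1.2 already refers to, by arm at Weeks 24 and 56. That would also bring the two sections into line.

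The cost is a sentence in the SAP and one changed or additional table. No new data are needed, and the borderline grouping can stay as written.

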4.2.10.5 Physical examination

Any new or aggravated clinically relevant abnormal medical finding at a physical examination as compared with the baseline assessment will be reported as an AE unless unequivocally related to the disease under study and will be summarised as described in Section [4.2.10.1](#).

4.2.11 Impact on analyses due to COVID-19 pandemic

The study is conducted during the COVID-19 worldwide pandemic. Patient dosing, scheduled visits, and nasal endoscopies all may become difficult or impossible to perform according to protocol for patients being followed up in the study.

Efforts are ongoing to collect outstanding data via alternative means where possible, when on-site visits cannot be performed. Additionally, protocol deviations, including doses or visits missed due to COVID-19 related protocol deviations will be described separately in the CSR. These deviations will be identifiable in the database with a ‘COVID’ prefix.

5. INTERIM ANALYSES

No interim analysis is planned for this study.

6. CHANGES OF ANALYSIS FROM PROTOCOL

Not applicable.

8. APPENDIX

8.1 Missing data descriptions

Some patients may drop out prematurely, potentially leading to missing data. The amount of missing data is minimized as the protocol encouraged patients to attend study visits until they complete the overall study duration after they discontinue from randomized therapy. This section summarizes how we will describe the pattern of, and reasons for, missing data. It will also describe how we plan to account for missing data to assess the robustness of the treatment effect under different underlying missing data assumptions.

Tabular summaries for the percentage of patients by the reason for discontinuation of randomized treatment as well as for withdrawal from the study will be presented by treatment to describe why patients discontinue from randomized treatment or withdraw from the study. The time to discontinuation of randomized treatment will be presented using Kaplan Meier plot. Dependent on these outputs additional exploratory analyses covering the DB period may be produced to further understand the pattern of missing data.

8.2 Supplementary analysis: primary estimand with WP for surgery for CRSwNP only

As mentioned in Section 4.2.5.1, the primary analyses will be based on primary estimand. A supplementary analysis with a different strategy for the SCS use for CRSwNP will be conducted. This analysis will use a composite strategy for surgery only and will impute the WP only for patients with any surgery for CRSwNP at the time of their first surgery for CRSwNP. The occurrence of SCS use for CRSwNP will not be considered rescue and a treatment policy strategy will be used instead. Data prior to any surgery for CRSwNP will be included regardless of the use of SCS for CRSwNP. The same multiple imputation strategy as described in Section 4.2.5.1 will be carried out, but patients who receive SCS for CRSwNP but never have surgery for CRSwNP will be included in the MI step for non-rescued patients. See [Table 14](#) for random seeds to be used for this supplementary analysis.

8.3 Sensitivity analysis: primary estimand assuming dropout reason-based multiple imputation approach

As mentioned in Section 4.2.5.1, the primary analyses will be based on primary estimand. If a patient has a surgery and/or a course of SCS for CRSwNP, the data will be censored at the time of the first surgery and/or SCS use for CRSwNP, and the worst-possible value (after

surgery for CRSwNP) or the patient’s worst-observed value (after SCS for CRSwNP) will be imputed from that point until Week 56. A sensitivity analysis under the primary estimand with missing data imputed based on different withdrawal reasons will be conducted. As in Section 4.2.5.1, a composite strategy will be used for patients who have surgery and/or receive SCS for CRSwNP. For patients that do not undergo surgery or receive SCS for CRSwNP, missing data will be imputed using controlled sequential multiple imputation methods based on pattern mixture models (EMA/CHMP/EWP 2010). See Table 14 for random seeds to be used for this sensitivity analysis. This model will assume that some pre-specified subset of patients who withdraw from the study have correlations with future unobserved visits similar to patients in the placebo arm. The assumptions that will be used to impute the missing data are as follows:

- (a) Missing at Random (MAR): Assumes that the trajectory for patients who dropped out in each arm is similar to those observed in their own treatment arm. (The primary analysis already implements this approach. It will not be repeated.)
- (b) Dropout Reason-based Multiple Imputation (DRMI): Assumes that the trajectory for patients in the benralizumab arm who dropped out for a treatment related reason and/or severe non-compliance of protocol is similar to that of patients in the placebo arm, whereas the remaining patients who has dropped out are imputed assuming MAR.

A summary of reasons for patients withdrawing from the benralizumab treatment arm and the corresponding treatment arm used to calculate the imputation under MAR, and DRMI are given in Table 12 .

Table 12 Parameters for calculating the imputation under MAR, and DRMI

Reason for withdrawal	MAR	DRMI
Adverse Event	Benralizumab	Placebo
Development of study-specific discontinuation criteria*	Benralizumab	Placebo
Death	Benralizumab	Placebo
Severe non-compliance to protocol	Benralizumab	Placebo
Eligibility criteria not fulfilled	Benralizumab	Benralizumab
Patient lost to follow up	Benralizumab	Benralizumab
Patient decision	Benralizumab	Based on review prior to study unblinding
COVID-19	Benralizumab	Benralizumab
Other	Benralizumab	Based on review prior to study unblinding

Note: Patients in the placebo arm are imputed using non-missing values in placebo arm.

*Development of study-specific criteria for discontinuation are based on the following: Anaphylactic reaction to the investigational product requiring administration of epinephrine; Development of helminth parasitic infestations requiring hospitalisation; A respiratory-related event requiring mechanical ventilation.

Some reasons for withdrawal are clearer to determine as treatment related (AEs, death, development of study-specific discontinuation criteria) or non-treatment related (patients lost

to follow up, eligibility criteria not fulfilled). Other reasons are less clear such as patient decision and 'Other'; a review of each patient who withdraws from the study will therefore be carried out prior to unblinding the study. Based on this review the default assumptions for DRMI as described in b), and Table 12 may be changed. A list of these patients and the assumptions made under DRMI will be documented prior to unblinding of the study.

8.4 Supplementary analysis under the effectiveness estimand

A supplementary analysis will be evaluated under the effectiveness estimand. This analysis includes data collected up until the time of discontinuation from study treatment and excludes data if a patient has a surgery and/or SCS use for CRSwNP. Because these data will be analysed by ANCOVA for repeated measures which implicitly accounts for missing data under the MAR assumption, no imputation will be done after discontinuation from treatment or after rescue by surgery and/or SCS use for CRSwNP. This analysis evaluates the effect of initially assigned randomised treatment as long as the patient remains on treatment without being rescued by a significant alternate course of therapy such as surgery or SCS for CRSwNP.

The analysis will be conducted using ANCOVA for repeated measures with treatment arm, baseline scores (baseline total NPS for NPS model and baseline NBS for NBS model), visit, region, CCI and treatment×visit as covariates. The variance-covariance matrix will assume to be unstructured. If the procedure does not converge, then the Toeplitz, first-order autoregressive, and compound symmetric structure of variance-covariance matrices will be tried in that order. The estimate of the treatment effect will be based on a contrast from the repeated measures ANCOVA model.

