1.4 Number of patients

The primary analysis will compare the effect of benralizumab vs placebo on the change from baseline in total NPS at Week 56 and on the change from baseline in bi-weekly mean NBS at Week 56 using a hybrid of worst-possible/worst-observation carried forward and multiple imputation (MI), followed by an analysis of covariance (ANCOVA) with treatment arm,

baseline scores of the corresponding endpoint, region, CCI [REDACTED] as covariates (See Section 4.2.5.1 for details).

Approximately 250 patients will be randomised into SC benralizumab 30 mg or placebo in a 1:1 ratio.

The sample size was estimated based on a 2-sided t-test at a significance level of 0.05. Assuming the population standard deviation (SD) of change from baseline is 2 for total NPS and 1 for NBS, this sample size will provide an overall 80% power to detect a true mean (population) treatment difference of 0.85 units in total NPS and a difference of 0.4 in NBS with a two-sided 0.05 alpha level.

Based on the assumptions above, the minimum observed mean difference of the changes from baseline between benralizumab and placebo that would be statistically significant at the 0.05 level is -0.50 in total NPS and -0.25 in NBS.

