4.2.9 Exploratory efficacy variables

All exploratory efficacy endpoints will be collected during the double blinded period according to the SoA Table 2 in the CSP, except asthma exacerbation will be further collected during the OLE period (CSP Table 3). Therefore following analyses specified in Section 4.2.9.1 to Section 4.2.9.5 only apply to the double blind period at the primary DBL. Asthma exacerbation during the OLE period will descriptively summarized at final DBL.

4.2.9.1 Asthma control questionnaire 6

The observed mean ACQ-6 and the changes from baseline will be summarised by treatment group and by visit using descriptive statistics for all patients in PFAS in DB period.

The changes from baseline in mean ACQ-6 will be analysed under the treatment policy estimand where all data observed through Week 56 is included regardless of treatment discontinuation, surgery or SCS use for CRSwNP. The analysis will be conducted using ANCOVA for repeated measures (assuming missing at random) with treatment arm, baseline ACQ-6 scores, visit, region, CCI [REDACTED] and treatment×visit as covariates. See Appendix 8.5 for more details.

The ACQ-6 responder at Week 24 and at Week 56 will be analysed using the logistic regression with treatment arm, baseline ACQ-6, region, CCI [REDACTED] as covariates.

Observed data will be used; subjects with missing or non-evaluable observations at the timepoint of interest are counted as non-responders.

The number and proportion of responders and the number and proportion of patients by asthma control status will be summarised by treatment group for all patients in PFAS.

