8.5 Supplementary analysis under the treatment policy estimand

The co-primary endpoints will be evaluated under the treatment policy estimand during DB period. The treatment policy estimand includes data collected after discontinuation of study treatment regardless of rescue by surgery or SCS use for CRSwNP. Because these data will be analysed by ANCOVA for repeated measures which implicitly accounts for missing data under the MAR assumption, no imputation will be conducted for the missing data. The treatment policy estimand evaluates the treatment effect at the planned endpoint of the study, regardless of the treatments that patients actually received.

The analysis will be conducted using ANCOVA for repeated measures with treatment arm, baseline scores (baseline total NPS for NPS model and baseline NBS for NBS model), visit, region, CCI and treatment×visit as covariates. The variance-covariance matrix will assume to be unstructured. If the procedure does not converge, then the Toeplitz, first-order autoregressive, and compound symmetric structure of variance-covariance matrices will be tried in that order. The estimate of the treatment effect will be based on a contrast from the repeated measures ANCOVA model.

It is noted that if the primary analysis is statistically significant, it is not necessarily expected that all sensitivity and supplementary analyses will also give statistically significant results. If the results of the sensitivity/supplementary analyses provide reasonably similar estimates of

the treatment effect to the primary analysis, this will be interpreted as providing assurance that neither the lost information nor the mechanisms which cause the data to be missing have an important effect on primary analysis conclusions. Based on these outputs and the drug's mechanism of action, the plausibility of the assumptions that are made about missing data in the different analyses will be considered and described in the clinical study report.

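### If the unstructured covariance fit fails in SAP 8.4 or 8.5, the fallbacks force one variance on all visits with no robust standard error, so Week 56 intervals for NBS and DSS can be miscalibrated

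*SAP*

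**What the plan says.** SAP 8.4 (effectiveness estimand) and 8.5 (treatment policy estimand) fit a repeated-measures ANCOVA to change from baseline, with a treatment-by-visit interaction. The treatment effect is a contrast from that model. Both sections begin the same way: "The variance-covariance matrix will assume to be unstructured". Both then give the same fallback: "If the procedure does not converge, then the Toeplitz, first-order autoregressive, and compound symmetric structure of variance-covariance matrices will be tried in that order". Neither section names a heterogeneous version of these structures, the type of standard error or the degrees-of-freedom method.

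The text of both sections names NPS and NBS. The table in SAP 8.10 extends them to DSS and SNOT-22. ACQ-6 is brought in by SAP 4.2.9.1, which ends its model description with "See Appendix 8.5 for more details". SAP Table 4 windows the diary items, including NBS and DSS, every two weeks up to Week 56. SAP Table 3 gives NPS five post-baseline windows.

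**The concern.** Plain Toeplitz, first-order autoregressive and compound symmetric matrices each carry a single variance. If the true variance differs between visits, the model-based standard error of the Week 56 contrast reflects the variance pooled over all visits instead of the variance at Week 56. A pooled value below the Week 56 value makes the interval too short, and a pooled value above it makes the interval too long.

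A rise is plausible for NBS. Inclusion criterion 13 requires a bi-weekly mean of at least 1.5 on a 0-3 scale, so baseline lies between 1.5 and 3.0. Its SD therefore cannot exceed half that range, 0.75, whereas the planning SD for the change is 1. This entry-floor argument does not carry over to DSS, which has no such criterion.

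At stake is how far readers can rely on the Week 56 intervals and p-values from two supplementary analyses of a co-primary endpoint and of the first key secondary endpoint.

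**Working it through.** **Inputs from the documents (SAP 1.4).** A two-sided test at 0.05; about 250 patients allocated equally, taken here as 125 per arm; target differences of 0.85 (NPS) and 0.4 (NBS), with 80% power overall. Each endpoint has one planning SD and none by visit: "Assuming the population standard deviation (SD) of change from baseline is 2 for total NPS and 1 for NBS".

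**Plan's own figure.** The standard error of a difference is SD × √(2/125).
- NPS: 2 × 0.1265 = 0.253, and power = Φ(0.85/0.253 − 1.96) = 91.9%.
- NBS: 1 × 0.1265 = 0.1265, and power = Φ(0.4/0.1265 − 1.96) = 88.5%.
- The product is 81.4% (81.0% with the t distribution), against 80% stated.
- The minimum significant differences are 1.96 × 0.253 = 0.496 and 1.96 × 0.1265 = 0.248, against 0.50 and 0.25 stated.

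The figures reproduce. They also set the reference: with SD 1 at Week 56 and no dropout, the correct standard error for NBS is 0.126.

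**Number of covariance parameters.** Weeks 2, 4, …, 56 are 56/2 = 28 visits, so an unstructured matrix has 28 × 29/2 = 406 parameters. For NPS it is 5 × 6/2 = 15. In 8.4 the late visits also lose data after treatment discontinuation, surgery or SCS.

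**Effect of a common variance.** With complete data and a separate mean for each arm and visit, a compound symmetric fit gives

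ratio = model SE / true SE = √(mean of the visit variances) / SD at Week 56,

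and coverage ≈ 2Φ(1.96 × ratio) − 1.
- SD rising linearly from 0.5 to 1.0 over 28 visits: mean variance 0.585, ratio 0.76, coverage 86.6%.
- SD rising linearly from 0.7 to 1.0: mean variance 0.731, ratio 0.85, coverage 90.6%.

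**All three fallbacks.** The documents give no SD by visit and no dropout rate, so everything in this step is assumed. For each SD path (ending at 1.0 at Week 56), the large-sample best-fitting Toeplitz, AR(1) and compound symmetric matrix was found, and its model-based standard error was compared with the true one. Two correlation patterns were used, 0.4 + 0.55·exp(−lag/16) and 0.9·exp(−lag/40) with lag in weeks, each with dropout of 0% and 15% (completely at random). Ranges are over structure, correlation pattern and dropout.

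| Assumed SD path | Model SE / true SE | Coverage of nominal 95% interval |
|---|---|---|
| Linear rise 0.5 to 1.0 | 0.73-0.77 | 85.0-87.0% |
| Linear rise 0.7 to 1.0 | 0.82-0.86 | 89.3-90.7% |
| Early rise from 0.5, then plateau at 1.0 | 0.91-0.94 | 92.4-93.5% |
| Constant 1.0, no dropout | 1.00 | 95.0% |
| Constant 1.0, 15% dropout | 0.96-1.01 | 94.1-95.2% |
| Peak of 1.15 mid-study, then 1.0 | 1.04-1.10 | 95.9-96.8% |
| Fall 1.2 to 1.0 | 1.06-1.12 | 96.2-97.1% |

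**What a correct standard error would be.** Under the true covariance it is 0.126 with no dropout and 0.133-0.134 with 15% dropout. The heterogeneous structures were not fitted separately.

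**The case against.** The strongest reply is that narrow intervals need three things together: the unstructured fit fails, the standard errors are model-based, and the Week 56 variance exceeds the pooled variance. The documents establish none of these. Having 406 parameters does not imply failure: 250 patients and 28 visits allow up to 250 × 28 = 7,000 bi-weekly means, and an unstructured matrix may well be estimable. The SAP is silent on the type of standard error, which is a gap and not a plan to use model-based errors. Constant variance gives correct coverage, and falling or mid-peaking variance gives intervals that are too wide. All of this stands, and it is why the point is conditional.

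The role of these analyses also limits the point. SAP 4.2.5.2 lists one sensitivity and three supplementary analyses, and only two of these four use this model. SAP 8.5 does not expect every one of them to reach significance and judges them on whether the estimates are reasonably similar. ACQ-6 is exploratory and collected at site visits, so the 406-parameter argument does not reach it.

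A reader might infer that the plan's Week 56 intervals are too narrow, or that type I error is inflated. The documents support neither. No SD by visit is given, and the tests in SAP 4.1.3 come from other models: ANCOVA after worst-possible/worst-observation imputation and multiple imputation for the co-primary endpoints, DSS and SNOT-22, and ANCOVA without multiple imputation for LMS.

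The reply does not remove the rule itself. If the fallback is reached, it imposes equal variances without a safeguard, and readers will look at the intervals as well as the estimates.

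**Conclusion.** The point holds as a conditional weakness in two supplementary analyses. If the unstructured matrix does not converge, which is a realistic risk for NBS and DSS but not for NPS, the stated rule imposes a common variance and specifies no protection for the standard error. With model-based errors, coverage of a nominal 95% interval at Week 56 is about 85-87% or 89-91% under the two assumed linear rises, and 92.4-93.5% if the SD rises early and then levels off. It is about 95% if the SD is constant and 96-97% if it falls or peaks mid-study. Direction and size rest on assumed SD paths. A rise is plausible for NBS but cannot be read from the documents.

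The calculation is large-sample, uses assumed correlations and dropout completely at random, and models only arm-by-visit means. It says nothing about bias: with dropout at random, a wrong covariance could also shift the estimate, and this was not quantified. The multiplicity-controlled results and the sample size are not affected.

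**What to change.** In SAP 8.4 and 8.5, replace the fallback order with heterogeneous Toeplitz, then heterogeneous first-order autoregressive (ARH(1)), then heterogeneous compound symmetry (CSH). State that empirical (sandwich) standard errors are used whenever the unstructured matrix is not. The same sentence can name the degrees-of-freedom method. Both parts are useful: the heterogeneous structures address the covariance itself, while the sandwich estimator corrects only the standard error.

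The cost is one sentence and a model option, set before unblinding so that the covariance is not chosen after seeing results. Intervals may be slightly wider. Where the variance does rise, the widening is the correction itself. A baseline-by-visit term or coarser visits would be modelling preferences with no quantified gain, and the point does not depend on them.
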